the study, as well as the number and types of events (i.e. AEs, TEAEs, ADRs, Serious Adverse Events (SAEs)) of events will be summarized according to SOC and PT of MedDRA dictionary.

A patient with multiple AEs within a SOC will only be counted once towards the total of the SOC.

Descriptive statistics will be computed for all other safety endpoints (i.e., vital signs, physical examination, laboratory test, local tolerability-Application site signs/symptoms, overall application site irritation) at applicable time points, as well as changes from baseline by treatment arm.

Patient data listings will be provided as appropriate.

The analysis of baseline and demographics' characteristics will be performed on the RND population. The primary and secondary analyses will be performed on the FAS having the PP as supportive for the primary analysis. The safety analyses will be performed on the SAF.

More details on the statistical analyses will be provided in the Statistical Analysis Plan (SAP).

Date of issue

24JAN2025 (UK)

Signatures of Sponsor

Title A phase III study to assess efficacy and safety of N-Acetyl-GED-0507-34-LEVO gel █%, applied once daily for 12 weeks in patients with acne vulgaris (GEDACNE-1)

Protocol no: NAC-GED-0507-ACN-01-23-A

Protocol version: Final V2.0 (UK only)

Protocol date: 24JAN2025

Document History:

Version	Date	Description of change	Reason for change
1.1	17MAY2024	Original Version	NA
1.2	13AUG2024 (UK ONLY)	Harmonized the information in par. 10.3 with the Patient Information Sheet, in respect of information on treatment choices available to participants, and who they should contact in the circumstances they experience worsening acne. Added in paragraph 5.5.1 that the study visits for school age children should be undertaken outside of school hours. Minor improvements in Appendix C. Minor typos corrections.	MHRA RFI
2.0	24JAN2025 (UK ONLY)	Text added/modified to make processes and procedures more clear. Minor typos corrections.	Need to align the UK version with the one applied in the EU countries

This clinical trial protocol was subject to critical review and has been approved by the Sponsor. The information it contains is consistent with:

- the current risk-benefit evaluation of the investigational product

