- Collection of IMP and diary and assessment of patient compliance by diary check, and counting of tubes
- Schedule next visit.

Follow-up

Visit 6 (Wk14) End of trial Day99 (+ 2days) or ETV in case of withdrawal after EoT – Telephone contact

- Check concomitant medications/therapies and AEs
- End of trial.

If clinically significant out of range or clinically significant values are found at V5, patient will be asked to return at site to perform additional laboratory examinations of the significant out of range values.

This visit will be performed only for patients who are not included in the long-term study.

UNSCHEDULED VISITS (Early termination visit [ETV])

Any time the trial is permanently discontinued for any reason during the treatment phase, an Early Termination visit should be performed:

- Check concomitant medications/therapies and AEs
- Physical examination and measurements of vital signs (blood pressure and heart rate [pulse])
- Collection of samples for determination of laboratory parameters:
 - Standard safety laboratory examinations
 - Blood pregnancy test in childbearing potential women (see **Appendix C** for definition of WOCBP)
- Clinical assessments (lesion count [inflammatory and non-inflammatory lesions] and IGA/PGA). PGA will be evaluated only if the trunk is treated
- [REDACTED]
- [REDACTED] (not mandatory, following specific consent)

- Dermatology Life Quality Index (DLQI) / Children's Dermatology Life Quality Index (C-DLQI for patients from 9 to 16 years old), completed by the patient (prior to any Investigator assessments to not impact the patient's answers to the quality of life questionnaire)
- Evaluation of local tolerability signs/symptoms. The patient will be questioned if he/she experienced any of these subjective symptoms within the last 24 hours prior to visit
- Patient's assessment of overall application site irritation
- Collection of IMP and diary and assessment of patient compliance by diary check, and counting of tubes
- End of trial.

In case the discontinuation is during the Follow-up phase, the Visit 6 (Wk14) End of trial (± 2 days) – Telephone contact procedures will be performed.

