5.5.3. Measurement of safety parameters

Relevant medical history and AEs will be recorded.

Spontaneously noted complaints will be recorded along with their duration, intensity and probability of a correlation with the IMP (see Section 7.3, Evaluation of adverse events).

Laboratory examinations

The following laboratory parameters will be collected at screening (V1) and at the end of the comparative treatment phase (V5/Wk12, EoT) (see **Table 12**).

If clinically significant out of range or clinical significant values are found at V5, additional laboratory examinations will be performed at V6 (Follow-up/ETV visit).

Table 12: Laboratory examinations

Parameter	Screening examination V1 Day -14 to -1	Final examination V5 Wk12, Day 85 + 3 days (EoT)	ETV
Hematology			
RBC	X	X	X
WBC	X	X	X
Hemoglobin	X	X	X
Hematocrit	X	X	X

Parameter	Screening examination V1 Day -14 to -1	Final examination V5 Wk12, Day 85 + 3 days (EoT)	ETV
MCH	X	X	X
MCV	X	X	X
MCHC	X	X	X
Platelets	X	X	X
CBC/Differential	X	X	X
Clinical Chemistry			
AST (GOT)	X	X	X
ALT (GPT)	X	X	X
Total cholesterol	X	X	X
Triglycerides	X	X	X
HDL-C	X	X	X
LDL-C	X	X	X
Plasma glucose	X	X	X
████████████████████	X	X	X
████████	X	X	X
Pregnancy test	X	X	X
Fasting status	X	X	X

Hematology, clinical chemistry examinations and pregnancy test will be performed centrally.

Details on all laboratory procedures, collections, shipment of samples and reporting of results, alerting of extreme values and notable values by the central laboratory will be provided to investigators in the laboratory manual. The central laboratory will provide the sponsor with a copy of the laboratory certification and tabulation of the reference ranges. Details on collection and handling of laboratory samples are provided in the laboratory manual/instruction.

Any out of range laboratory results that are deemed clinically significant by the investigator will be recorded as medical history if detected at screening.

In case of unexpected laboratory out-of-range values in the blood samples collected at screening, which in the Investigator's opinion may pose the patient at increased risk during participation to the clinical trial, the patient/parents (or only one parent depending on local regulations) will be contacted to discontinue the treatment and will be withdrawn from the study. At all visits clinically significant laboratory results will be recorded as AEs.

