6.4. Safety and tolerability endpoints

1. Incidence of all Adverse Events (AEs), Treatment-Emergent Adverse Events (TEAEs), Adverse Drug Reactions (ADRs), Serious Adverse Events (SAEs) throughout the study with special attention to local TEAEs concerning the treated facial area (local dermal safety), and systemic TEAEs
2. Frequency of discontinuation of treatment due to TEAEs
3. Changes from baseline of vital signs during the study
4. Physical examination during the study
5. Changes from baseline of laboratory test at V5/Wk12
6. Change from baseline of local tolerability- Application site signs/symptoms during the

study*

7. Assessment of overall application site irritation at V5/Wk12.

*Local tolerability will be evaluated on the basis of the following signs and symptoms: application site non-lesional erythema, application site exfoliation, and application site dryness, stinging, burning, itching. For each sign/symptom, a severity score will be assigned using a 4-point scale from 0 = absent to 3 = severe.

Only a sign/symptom occurring after the first application of study medication that requires additional therapy or discontinuation of treatment or judged clinically significant by the Investigator, will be documented as a TEAE.

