6.6.2. Safety analyses

The analysis of safety will be conducted on the Safety Set.

Adverse events (AEs) will be coded by System Organ Class (SOC) and Preferred Term (PT), using the Medical Dictionary for Regulatory Activities (MedDRA).

Treatment-emergent adverse events (TEAEs), i.e. AEs with an onset on or after the time of the first IMP application, will be analyzed. TEAEs will be summarized by primary system organ class (SOC), preferred term (PT), severity and relationship to IMP.

All local tolerability signs and symptoms (both objective and subjective) will be listed and summarized at each visit by treatment and severity using frequency tables.

The overall application site irritation requested at the end of the study treatment will be listed and summarized using frequency tables by treatment group.

Vital signs will be listed and presented descriptively by visit, including changes from baseline.

Regarding laboratory assessments, the overall investigator's interpretation (as normal [N], abnormal but not clinically significant [NCS] or abnormal and clinically significant [CS]) will be listed and summarized by treatment group using shift tables from Visit 1 to Visit 5/Wk12.

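### The laboratory endpoint and its shift table both end at V5/Wk12, so laboratory results taken at the early termination visit have no place in the by-arm summaries

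*Protocol*

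**What the plan says.** The laboratory endpoint in section 6.4, item 5, is "Changes from baseline of laboratory test at V5/Wk12". The synopsis lists the same endpoint.

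For its analysis, section 6.6.2 takes the investigator's overall three-level interpretation, which "will be listed and summarized by treatment group using shift tables from Visit 1 to Visit 5/Wk12". It mentions no numeric laboratory summary. Just before that it says: "Vital signs will be listed and presented descriptively by visit, including changes from baseline".

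The synopsis, under its safety analysis, is wider: "Descriptive statistics will be computed for all other safety endpoints (i.e., vital signs, physical examination, laboratory test" and further endpoints), "at applicable time points, as well as changes from baseline by treatment arm". Section 6.6 adds a general rule that continuous data are summarised by mean, SD, median, IQR and range, by arm and, where relevant, by visit.

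On sampling, section 5.5.3 says: "The following laboratory parameters will be collected at screening (V1) and at the end of the comparative treatment phase (V5/Wk12, EoT"). Its Table 12 also has an ETV column, marked for every parameter. The ETV list in section 5.5.1 includes "Collection of samples for determination of laboratory parameters", and the schedule in Appendix A agrees.

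**The concern.** The patients who stop early are the ones for whom a laboratory summary matters most. Section 8.3.1 lists adverse events among the reasons for leaving, and one further reason is itself a laboratory finding: out-of-range screening values that the investigator judges to raise the patient's risk. If the by-arm tables show only patients who reached V5, they describe those who tolerated twelve weeks of treatment. If stopping differs between arms, the comparison is made on a selected group, although a sample from the others was planned and may well have been taken.

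A second, smaller matter is that section 6.6.2 does not describe the analysis of the endpoint that section 6.4 defines. A shift in an overall clinical judgement is not a change from baseline in a measured value. Anyone writing tables from section 6.6.2 alone would produce only the former.

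**Working it through.** No arithmetic applies: the plan states no figure on this point, and the drop-out rate is redacted. The check is to follow one early terminator's laboratory sample through the protocol.

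1. **Does the patient reach V5?** No. Section 8.3.1 requires anyone who stops IMP permanently, whatever the cause, to be discontinued, and asks for the ETV procedures as far as possible. In section 5.5.1 the ETV closes with the end of the trial, so no V5 follows.
2. **Is a laboratory sample planned?** Yes. Section 5.5.1, Table 12 in section 5.5.3 and Appendix A all place safety laboratory tests at the ETV.
3. **Is the patient in the safety population?** Yes. Under section 6.2 the Safety Set contains everyone who received at least one dose, and section 6.6.2 analyses safety on that set.
4. **Does the result enter the shift table?** Not as written. The table runs from Visit 1 to Visit 5/Wk12 and does not mention the ETV. The patient can appear only as missing at the end visit, or not at all.
5. **Does the result enter the numeric change?** Not as the endpoint is defined, since section 6.4 item 5 and the synopsis both fix it at V5/Wk12.
6. **Does another rule bring it in?** Section 6.7 carries observations forward only for lesion counts and IGA/PGA. It has no rule for laboratory data.
7. **What is left?** Section 5.5.3 says: "At all visits clinically significant laboratory results will be recorded as AEs". A clinically significant ETV result therefore reaches the adverse event tables. Other ETV results, including abnormal ones judged not clinically significant, can appear only in listings.

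The wording on the numeric summary compares as follows:

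| Place in the protocol | Laboratory analysis stated |
|---|---|
| Section 6.4 item 5 and synopsis endpoint | Change from baseline at V5/Wk12 |
| Synopsis, safety analysis | Descriptive statistics and change from baseline by arm, at applicable time points |
| Section 6.6 | Continuous data summarised descriptively (general rule) |
| Section 6.6.2 | Overall three-level interpretation, V1-to-V5 shift table and listing |

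The first three rows agree that numbers are to be summarised. Only section 6.6.2 does not say so. The V5 end point appears both in the endpoint and in section 6.6.2, so the gap for early terminators is not a by-product of choosing a shift table over a change score.

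**The case against.** The strongest reply is that nothing is truly lost. Section 6.6.2 is not exhaustive: it also leaves out physical examination and the frequency of discontinuation due to TEAEs, both endpoints in section 6.4. Its silence on numeric laboratory change is therefore not an exclusion, and no text gives it precedence over the synopsis or section 6.6. This stands. A reader might infer from section 6.6.2 that laboratory drifts within the normal range will go unseen. The documents do not support that, because the synopsis names laboratory tests among the endpoints summarised with changes from baseline by arm, and section 6.6 summarises continuous data in general. This half of the point is a wording mismatch.

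The reply continues that ETV results are covered by adverse event recording, by listings and by the synopsis phrase on applicable time points, and that visit mapping is ordinary SAP content. This stands only in part. Adverse event recording covers only clinically significant results, and a listing is not a comparison by arm. The synopsis phrase leaves room for the ETV without naming it, while the synopsis endpoint itself is fixed at V5/Wk12. Deferral to the SAP would be a full answer if the protocol were silent, but it names the end visit in both places. The opening of section 6 also says the SAP will be built on that description.

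**Conclusion.** The point holds as a minor one. As written, Safety Set patients who stop early have no place in the laboratory shift table or in the change at V5, although laboratory samples are scheduled for them at the ETV. Their clinically significant results survive as adverse events and the rest at most in listings. The missing numeric summary in section 6.6.2 is an inconsistency of wording, since the synopsis and section 6.6 retain that summary.

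The size cannot be given. A reader might infer it from the gap between 400 randomised and 366 evaluable patients, but that gap neither counts nor bounds missing V5 laboratory data: the FAS needs only one valid post-baseline efficacy assessment for both primary endpoints, so a patient who leaves after Week 4 can be in the FAS without a V5 sample. Nor can the loss be expressed as power, because the plan specifies no between-arm laboratory test.

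The conclusion assumes that the ETV sample is actually obtained, which section 8.3.1 asks for only as far as possible, and that the SAP, which is not at hand, follows the protocol wording. Data collection and the primary efficacy analysis are not affected.

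**What to change.** In section 6.6.2 and section 6.4 item 5, with the matching synopsis endpoint:

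- Run the shift table and the change from baseline from V1 to the last on-study value, meaning V5, or the ETV for patients who stop early. Show the ETV results separately as well, so that the Week 12 picture stays visible.
- State in section 6.6.2 that each laboratory parameter is summarised descriptively by arm, as value and as change from baseline, in line with the synopsis. Keep the three-level shift table beside it.

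No between-arm confidence interval or test is needed to meet section 6.4 or the synopsis.

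The cost is one or two sentences and a few more tables. The samples are already scheduled, so there is no extra burden on patients or sites. Exposure time will differ between V5 and ETV values, which is why the ETV results should also stand on their own.

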6.6.3. Interim analyses

Not applicable

6.7. Handling of dropouts and missing data

Last observation carried forward (LOCF) imputation methodology will be used to impute missing values for the lesions count and the IGA/PGA in the FAS set.

7. Adverse events

7.1. Evaluation of adverse events

An adverse event (AE) is any untoward medical occurrence in a patient to whom a medicinal product is administered and which does not necessarily have a causal relationship with this treatment (see Regulation (EU) No 536/2014).

Therefore, an AE can be any unfavorable and unintended sign (including an abnormal laboratory finding), symptom, or disease temporally associated with the use of a medicinal (investigational) product, whether or not related to the medicinal (investigational) product.

Worsening of acne, in the treated area, is not to be recorded as an AE unless it results in the discontinuation of the patient from the trial or the use of further treatment for acne.

The observation period for AEs extends from when the patient provides informed consent until the trial is completed. AEs still present after the last patient's scheduled visit will be followed up within 14 days of receiving the last IMP dose by means of a phone call or site visit, as considered appropriate. After that time point the need for additional follow-up of ongoing AEs/SAEs will be discussed between the investigator and the Sponsor. However, in the event of discrepancies, the investigator's criteria will prevail. AEs occurring after the end of the clinical trial must be reported if the investigator considers there is a causal relationship with the investigational product.

The investigator will be responsible for the necessary acute medical treatment of any AEs required during the trial and will ensure that appropriate medical care will be maintained thereafter, if necessary.

All patients experiencing AEs - whether considered related with the use of the IMP or not - will be monitored until symptoms subside and any abnormal laboratory values have returned to baseline, or until there is a satisfactory explanation for the changes observed, or until death, in which case a full pathologist's report will be supplied, if possible. "Related" means a reasonable possibility that the event may have been caused by the IMP. All findings will be reported on an "adverse event"/ "serious adverse event" page in the case report form.

All AEs, including intercurrent illnesses, will be reported and documented as described below.

AEs are divided into the categories "serious" and "nonserious". This determines the procedure for reporting/documenting the AE (see below).

Surgical procedures themselves are not AEs but therapeutic measures for conditions requiring surgery. The condition for which the surgery is required is an AE, if it occurs or is detected during the trial period. Planned surgical measures permitted by the clinical trial protocol and the condition(s) leading to these measures are not AEs, if the condition(s) was (were) known before the start of treatment with investigational product. In the latter case the condition should be reported as medical history.

7.2. Definition of serious and nonserious adverse events

A serious adverse event (SAE) is any untoward medical occurrence that at any dose:

- results in death or is life-threatening
- results in permanent or significant disability/incapacity
- requires inpatient hospitalization* or prolongation of hospitalization
- results in a congenital abnormality/birth defect.

Medical and scientific judgment will be exercised in classification of other important medical events that may not be immediately life-threatening or result in death or hospitalization but may jeopardize the patient or may require intervention to prevent one of the other outcomes listed in the definition above. These should also usually be considered serious.

AEs which do not fall into these categories are defined as nonserious.

**Hospitalization solely for the purpose of diagnostic tests, even if related to an AE, elective hospitalization for an intervention which was already planned before the inclusion of the patient in the clinical trial, and admission to a day-care facility may not themselves constitute sufficient grounds to be considered as a SAE.*

7.3. Reporting/documentation of adverse events

7.3.1. Reporting of adverse events

AEs either reported by the patient, or observed by the investigator **must be recorded on the adverse event page of the CRF** and should be described in the following manner:

The **nature** of the event will be described in precise, standard medical terminology (i.e. not necessarily the exact words used by the patient). A specific diagnosis should be stated (e.g., allergic contact dermatitis) if known.

The **intensity** of the AE will be described in terms of mild, moderate or severe according to the investigator's clinical judgment.

- **Mild:** The AE does not interfere in a significant manner with the patient's normal functioning level, but may be an annoyance
- **Moderate:** The AE produces some impairment of functioning but is not hazardous to health, but is uncomfortable and/or an embarrassment
- **Severe:** The AE produces significant impairment of functioning or incapacitation and is a hazard to the patient.

The **duration** of the event will be described by the start date and end date.

The **location** for cutaneous AEs will be described as at or just around the application area (≤ 2 cm from the application area) or distant (>2 cm from the application area).

The **causal relationship** between the event and the use of the IMP will be described in terms of:

Certain: the AE

- occurs in a plausible time relationship to IMP administration, and cannot be explained by concurrent disease or other drugs or chemicals, and
- follows a clinically plausible response to withdrawal of the IMP, and
- is definitive based on recognized pharmacological or other parameter associated with the IMP, and
- is confirmed by rechallenge procedure, if performed.

Probable: the AE

- follows a reasonable temporal sequence from administration of the IMP, and
- is unlikely to be attributed to a disease or other drug/s, and
- disappears or decreases on withdrawal of the IMP.

Possible: the AE

- follows a reasonable temporal sequence from administration of the IMP, but
- can also be explained by disease or other drugs, and
- information on drug withdrawal may be lacking or unclear.

Unlikely: the AE

- does not follow a reasonable temporal sequence from administration of the IMP, and
- can be reasonably explained by disease or other drug/s, and
- does not follow a known pattern of response to the IMP, and
- does not reappear or worsen upon re-challenge, if performed.

Not related: the AE

- occurs prior to IMP administration.

The **outcome** of the event will be described in terms of:

- Recovered/resolved
- Recovering/resolving
- Recovered/resolved with sequelae
- Not recovered/not resolved
- Fatal
- Unknown.

It will also be recorded if the study product use is continued, interrupted or discontinued.

Note: Insofar as possible all AEs should be followed-up to determine the final outcome of the event. Details of follow-up should be given (e.g., discontinuation of IMP, if specific treatment is required, if hospitalization is required etc.).

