3.2. Stress/risks due to the investigational medicinal product (IMP)

Pre-clinical considerations

On the basis of the available non-clinical and clinical data, there is no evidence that using N-Acetyl-GED-0507-34-Levo gel will raise to major safety concerns.

In the embryo-fetal development toxicity studies performed in the rat and in the rabbit and in the fertility study performed in the rat, no adverse effects were observed on embryofetal development, teratogenicity and on fertility parameters, upon systemic exposure of animals to very high NAC-GED-0507 plasma concentrations.

Negative results were obtained in all genotoxicity studies performed with both NAC-GED-0507 and GED-0507.

The UV-Vis spectra recorded on NAC-GED-0507 ■% gel and the results obtained by testing NAC-GED-0507 in the Balb/C 3T3 Cell Phototoxicity Assay with neutral red uptake, are predictive of no phototoxicity.

Clinical considerations

NAC-GED-0507 ■%, ■% and ■% topical formulation proved safe in the clinical studies performed in acne patients upon a 12-week treatment, and negligible systemic absorption (below LLOQ of ■ ng/mL) was observed for the formulation with higher dosage.

Overall, clinical data confirm a very good safety profile of NAC-GED-0507 ■% when administered for 12 consecutive weeks, poorly distinguishable from the safety profile of vehicle. In a large randomized double blind controlled clinical trial (NAC-GED-0507-ACN-01-18), the percentage of patients who had one or more AEs was 19%, 16% and 19% in the NAC-GED ■%, NAC-GED ■% and vehicle groups, respectively.

Considerations about safety in children

Based on the following considerations, a positive opinion for the Paediatric Investigation Plan (EMA-002674-PIP01-19) in a population from 9 years to less than 18 years of age was awarded by the Paediatric Committee (PDCO) of the European Medicines Agency.

Negligible systemic absorption upon administration of NAC-GED-0507 ■% gel for 12 consecutive weeks has been demonstrated in the performed clinical study NAC-GED-0507-ACN-02-17 in acne patients aged ≥ 12 years. Moreover, a favorable safety and local tolerability profile of NAC-GED-0507 gel has been demonstrated in acne patients aged ≥ 12 years.

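### The causality scale reserves 'Not related' for events before the first dose, so no treatment-emergent event can be rated unrelated, and coincidental events can end up as 'Possible'

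*Protocol*

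**What the plan says.** Section 7.3.1 has the investigator rate each adverse event in one of five categories: *Certain*, *Probable*, *Possible*, *Unlikely* or *Not related*. The relevant definitions are:

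- *Not related* has a single criterion, that the event "occurs prior to IMP administration". The text then moves straight to the outcome categories, so nothing appears to be lost.
- *Unlikely* is a list joined by 'and'. Its first item is that the event "does not follow a reasonable temporal sequence from administration of the IMP, and".
- *Possible* takes an event with reasonable timing that "can also be explained by disease or other drugs, and" for which withdrawal information may be missing or unclear.

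Section 7.1 says that related "means a reasonable possibility that the event may have been caused by the IMP".

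On use of the ratings, section 6.6.2 defines TEAEs as "AEs with an onset on or after the time of the first IMP application" and states that "TEAEs will be summarized by primary system organ class (SOC), preferred term (PT), severity and relationship to IMP". Section 6.4 lists as its first safety endpoint the "Incidence of all Adverse Events (AEs), Treatment-Emergent Adverse Events (TEAEs), Adverse Drug Reactions (ADRs), Serious Adverse Events (SAEs) throughout the study".

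**The concern.** A causality scale needs a rating for an event that happens on treatment and has nothing to do with the treatment. This scale has none. The label that should carry that judgement repeats a timing fact already captured elsewhere: section 5.5.1 records events before the start of treatment as non-treatment-emergent, and section 6.6.2 separates TEAEs by onset.

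Two outputs depend on the rating. One is the relationship breakdown of TEAEs, together with ADR incidence as an endpoint. The other is the handling of serious events, because an unexpected serious event rated *Possible* may be processed as a suspected reaction under section 7.3.2.

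The rating is made by the investigator and recorded on the CRF. A later analysis plan can group the categories, but it cannot recover a judgement of no relation that the scale never allowed.

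**Working it through.** The protocol states no ADR rate, so there is no figure to reproduce. The check compares the definitions.

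**Step 1: *Not related* against TEAE.** *Not related* (7.3.1) requires onset before IMP. A TEAE (6.6.2) requires onset at or after the first application. The intersection is empty. No TEAE can be rated *Not related*, in either arm, because the vehicle is itself an IMP (IMP 2-V).

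**Step 2: where a coincidental post-dose event goes.** Take an ordinary cold in week 5 that the investigator believes is unrelated and that disease fully explains.

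| Category (7.3.1) | Deciding criterion | Timing accepted as reasonable | Timing judged not reasonable |
|---|---|---|---|
| *Not related* | onset before IMP | fails | fails |
| *Unlikely* | timing not reasonable, plus the other items | fails on the first item | open |
| *Possible* | timing reasonable, another explanation available | fits | fails |
| *Probable* | another cause improbable | fails | fails |
| *Certain* | no other explanation | fails | fails |

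With timing accepted, *Possible* is the only category whose wording fits. Its last condition, that withdrawal information may be missing, is easily met when a self-limiting event resolves while dosing continues. With daily application over 12 weeks (84 applications), an investigator can readily regard the timing of an on-treatment event as reasonable, though nothing in the protocol obliges that view.

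**Step 3: consistency with 7.1.** Section 7.1 ties relatedness to a reasonable possibility of causation, so a post-dose event without that possibility is unrelated. Section 7.3.1 gives no *Not related* rating for it and, in the left column of outcomes above, leads to *Possible*. The two sections disagree.

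**Step 4: bounds on the effect on ADR incidence.** The protocol does not say which categories make an ADR, so the effect can only be bracketed.

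- If ADR means *Certain*, *Probable* or *Possible*, the narrow *Not related* wording adds nothing by itself. Inflation arises only through the route in step 2, and its frequency depends on how investigators judge timing.
- If ADR means anything except *Not related*, every TEAE is an ADR. As an assumption, suppose the any-AE proportions of 16% to 19% that section 3.2 reports for the earlier Phase 2b study carry over. The ceiling is then 0.16 × 200 = 32 to 0.19 × 200 = 38 patients per arm.

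The bracket runs from no effect to all TEAEs. It is not an estimate.

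**The case against.** The strongest reply is that *Unlikely* remains available after dosing and that timing is a matter of judgement. Being on daily treatment is not the same as following a reasonable temporal sequence, and a sensible investigator need not accept a sprain as plausibly timed. The word 'also' in the *Possible* criterion suggests that the IMP must itself be a credible explanation, and the definition in 7.1 can be applied alongside the scale. This stands as a reason why the shift into *Possible* is not inevitable. It does not restore a usable *Not related* rating, and it leaves the cumulative criteria of *Unlikely* closed to an event with plausible timing.

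A reader might infer more: that ADR incidence is inflated in both arms and that a true difference between arms would be largely hidden. The documents do not support this. The size of the shift is unknown and the ADR mapping is not stated. Under randomisation, background events should be similar in the two arms. If they add the same amount b to ADR rates a and v, then (a + b) − (v + b) = a − v. The ratio is pulled towards 1, but the absolute difference does not collapse.

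Other safeguards limit the consequences. TEAEs are also summarised regardless of relationship, local tolerability is scored separately (5.5.2.6, 6.6.2), all serious events go to the sponsor within 24 hours (7.3.2), and no formal test of ADR rates is planned. Any error would be towards over-attribution.

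Finally, the mapping of categories to ADR is commonly left to the SAP, which is not at hand. Its absence from the protocol is not part of this point.

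**Conclusion.** The definition is wrong as written. It is certain, from the text alone, that no TEAE can be rated *Not related* and that this cell of the planned summary is empty by construction in both arms. It is also clear that 7.3.1 conflicts with 7.1, and that a coincidental event with accepted timing fits *Possible* by its wording.

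What follows for ADR incidence, and for which serious events are treated as suspected reactions, is a possibility and not a demonstrated bias. It depends on how investigators judge timing and on which categories are counted as ADRs, and the protocol fixes neither. The primary efficacy analyses are untouched. The point is still worth correcting, because the change is small and the missing judgement cannot be recovered by analysis once the ratings have been collected.

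**What to change.** In section 7.3.1 and the eCRF completion guideline, redefine *Not related* to include events after dosing for which there is no reasonable possibility of causation by the IMP, for example because there is a clear alternative cause or the timing is implausible. This matches section 7.1. Leave onset before the first dose to the TEAE flag, which already identifies it.

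The cost is a few lines in each document. The one drawback is that events already rated keep the old scale unless they are queried.
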